11.2. Assessment of Adverse Events

11.2.1. Adverse Event Severity

Intensity of all AEs will be graded according to NCI-CTCAE version 5 on a five-point scale (Grade 1 to 5) and reported in detail on the eCRF. Adverse events not listed on the CTCAE should be graded as follows:

- Grade 1: mild; asymptomatic or mild symptoms; clinical or diagnostic observations only; intervention not indicated
- Grade 2: moderate; minimal, local or non-invasive intervention indicated; limiting age-appropriate instrumental activities of daily living (ADL)*
- Grade 3: severe or medically significant but not immediately life-threatening; hospitalisation or prolongation of hospitalisation indicated; disabling; limiting self-care ADL**
- Grade 4: life-threatening consequences; urgent intervention indicated
- Grade 5: death related to AE

*NB: Instrumental ADL refers to preparing meals, shopping for groceries or clothes, using the telephone, managing money, etc.

**NB: Self-care ADL refers to bathing, dressing and undressing, feeding self, using the toilet, taking medications and not being bedridden.

11.2.2. Adverse Event Causality

The Investigator (or appropriately qualified designee) will determine the relationship of the AE to the study drug using all available data (including detailed history taking, comprehensive clinical and laboratory/imaging assessment, as appropriate), taking into account good clinical and scientific judgement and categorise as detailed in the following sections.

Related to Study Treatment

A ‘reasonable possibility’ of a relationship between an AE to the study treatment is considered if:

- It follows a reasonable temporal sequence from administration of the drug, or
- It could not readily have been produced by the patient’s clinical state, environmental or toxic factors, or other modes of therapy administered to the patients; or it follows a known pattern of response to the test drug

Study Number: SLN360-002	Compound No.: SLN360
Protocol	Version: 1.0

Not Related to Study Treatment

‘No reasonable possibility’ of a relationship between an AE to the study treatment is considered if:

- It is clearly related to extraneous causes, or
- It does not follow a reasonable temporal sequence from administration of the test drug, or
- It could readily have been produced by the patient’s clinical state, environmental or toxic factors, or other modes of therapy administered to the patients, or
- It does not follow a known pattern of response to the test drug, or
- It does not reappear when the drug is re-administered

Adverse events, medical history and concomitant procedures will be coded using the Medical Dictionary for Regulatory Activities (MedDRA) according to the version specified in the Data Management Plan. Prior and concomitant medications will be coded using the World Health Organization Drug Dictionary according to the version specified in the Data Management Plan.

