11.1.4. Adverse Drug Reactions

All noxious and unintended responses to an IMP (i.e., where a causal relationship between an IMP and an AE is at least a reasonable possibility) related to any dose should be considered adverse drug reactions.

Suspected unexpected serious adverse reactions (SUSARs) are SAEs, classed as related, which are not specified as expected in the approved IB. An unexpected adverse drug reaction is defined as an adverse reaction, the nature and severity of which is not consistent with the applicable product information (e.g., the IB for an unapproved IMP).

Study Number: SLN360-002	Compound No.: SLN360
Protocol	Version: 1.0

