3.5.1 Adverse Events (AEs)

All AEs will be coded to system organ class and preferred term using MedDRA. Treatment emergent adverse events (TEAEs) are defined as AEs that start after the first dose of study drug. Severity will be graded according to the National Cancer Institute Common Terminology Criteria for Adverse Events (NCI-CTCAE) on a five-point scale (Grade 1 to 5). Study drug-related AEs are defined as AEs considered by the investigator as having a reasonable possibility of being related to study drug.

An overview of TEAEs will be provided including counts and percentages of subjects (and event counts) with the following:

- Any TEAEs (overall and by maximum severity)
- Any study drug-related TEAEs (overall and by maximum severity)
- Any serious adverse events (SAEs)
- Any serious TEAEs
- Any study drug-related serious TEAEs
- Any TEAEs leading to discontinuation of study drug
- Any TEAEs leading to discontinuation of study
- Any TEAEs leading to death

Summary tables of TEAEs, TEAEs by maximum severity, study drug-related TEAEs, serious TEAEs and TEAEs leading to discontinuation of study drug or study will be provided with the number and percentage of subjects with adverse events and the number of events classified by primary system organ class, and preferred term.

System organ classes and preferred terms will be sorted alphabetically.

For tabulations that include classification by relationship to study drug, TEAEs with missing relationship will be considered related to study drug. For tabulations that include classification by severity, missing severity will be considered as the most severe TEAEs that are not SAEs.

Adverse event listings will be presented by subject, system organ class and preferred term.

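### The causality lists in Protocol 11.2.2 overlap without a precedence rule, and novelty alone is enough for Not related, so a novel serious reaction can be classed outside the SUSAR definition

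*Protocol*

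**What the plan says.** Protocol 11.2.2 asks the investigator, or a qualified designee, to judge causality on all the data and then sort the event under one of two lists.

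- **Related.** The first item is timing: "It follows a reasonable temporal sequence from administration of the drug, or". The second is met if the event could not readily be explained by the patient's condition, the environment or "other modes of therapy administered to the patients; or it follows a known pattern of response to the test drug".
- **Not related.** There are five items, again alternatives: "It is clearly related to extraneous causes, or"; "It does not follow a reasonable temporal sequence from administration of the test drug, or"; the event could readily have another cause; "It does not follow a known pattern of response to the test drug"; and "It does not reappear when the drug is re-administered".

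The section does not say what to do when an event meets an item on each list.

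Two later steps depend on the call. Protocol 11.1.4 says that SUSARs "are SAEs, classed as related, which are not specified as expected in the approved IB", and it judges unexpectedness by nature and severity against the product information. SAP 3.5.1 states: "Study drug-related AEs are defined as AEs considered by the investigator as having a reasonable possibility of being related to study drug". The drug-related TEAE and drug-related serious TEAE summaries in Protocol 12.4.4.2.1 and SAP 3.5.1 follow from that.

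**The concern.** The two lists lead to opposite conclusions, yet one event can satisfy both. Two investigators who both follow the text can class the same event differently, and about 40 centres are planned (Protocol 5.1).

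The known-pattern item is the more serious problem. A SUSAR has to be related and also not already described as expected. A reaction of a new kind has no known pattern, and 11.2.2 prints that as a sufficient reason to call it Not related. The causality rule and the SUSAR definition therefore pull against each other for the events that SUSAR reporting is meant to find.

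Knowledge of SLN360's response pattern is also limited. Protocol 1.1.3 describes one ongoing clinical study. Its single-dose part had 24 participants on SLN360, and none of the 32 enrolled had known overt cardiovascular disease. The present trial enrols people at high risk of atherosclerotic events.

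At stake are the consistency of the drug-related tables, in a trial whose larger sample is justified partly by safety evaluation (Protocol 12.3.1), and the classification of new serious reactions.

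**Working it through.** The plan gives no figure on this point, so the check is a truth table of the two lists as printed.

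**Features.** T = plausible timing. C = could readily have another cause. K = known response pattern. R = reappears on re-administration. The clearly-extraneous item is set to no.

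**Rules as printed.**
- Related = T or not C or K
- Not related = not T or C or not K or not R

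| Row | T | C | K | Related | Not related, R yes | Not related, R no | Not related without the K and R items |
|---|---|---|---|---|---|---|---|
| 1 | yes | no | yes | yes | no | yes | no |
| 2 | yes | no | no | yes | yes | yes | no |
| 3 | yes | yes | yes | yes | yes | yes | yes |
| 4 | yes | yes | no | yes | yes | yes | yes |
| 5 | no | no | yes | yes | yes | yes | yes |
| 6 | no | no | no | yes | yes | yes | yes |
| 7 | no | yes | yes | yes | yes | yes | yes |
| 8 | no | yes | no | no | yes | yes | yes |

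**Counts as printed** (8 rows × 2 states of R = 16 profiles).
- Related only: row 1 with R yes = 1.
- Not related only: row 8, both states of R = 2.
- Both: row 1 with R no, plus rows 2 to 7 in both states = 1 + 12 = 13.
- Neither: 0.

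If re-administration is left out altogether, rows 2 to 7 meet both lists: 6 of 8.

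**No known pattern** (rows 2, 4, 6 and 8; 8 profiles). All 8 meet Not related. Rows 2, 4 and 6 also meet Related, which is 6 of the 8.

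**The critical case is row 2:** plausible timing, no other ready cause, no known pattern. It meets Related on both timing and the lack of another cause. With R yes, it meets Not related on the known-pattern item alone.

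**Sensitivity to the model.**
- Add the extraneous-cause item (taken to imply another ready cause) and a third state, not re-administered. Of 36 profiles, 28 meet both lists, 6 only Not related and 2 only Related. Of the 18 without a known pattern, all meet Not related and 12 also meet Related.
- Without that implication, of 48 profiles 40 meet both, 6 only Not related and 2 only Related.
- If Related is read, against the printed 'or', as needing timing and the second item together, 10 of the 36 still meet both.

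**Effect of removing the K and R items from Not related** (last column; 16 profiles).
- Related only: rows 1 and 2 = 4.
- Not related only: row 8 = 2.
- Both: rows 3 to 7 = 10.

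Row 2 is then Related only. Since 10 profiles still overlap, a rule for events on both lists is also needed.

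**The case against.** A reader might infer that an event without a known pattern is automatically Not related, that every unexpected serious reaction meets that list, and that it then drops out of SUSAR reporting. The documents do not support any of the three.

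- **Not automatic.** Six of the 8 profiles without a known pattern also meet Related. The text leaves a choice, and 11.2.2 gives that choice to the investigator's judgement.
- **Not always.** Protocol 11.1.4 judges unexpectedness by nature and severity. A reaction of a known kind that is more severe than documented can follow a known pattern and still be unexpected.
- **Meeting an item removes nothing.** SUSAR status turns on how the event is actually classed. Protocol 11.3.2 sends every SAE to the sponsor within 24 hours whatever the suspected cause. The documents do not describe a sponsor causality review, but that does not show there is none.

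The effect on safety conclusions is also bounded. SAP 3.5.1 tabulates all TEAEs, serious TEAEs, discontinuations and deaths irrespective of causality, and counts a missing relationship as related. Liver tests and injection-site findings are summarised without a causality call (SAP 3.5.2 and 3.5.5). Suspected liver injury has its own structured assessment (Protocol 11.2.3), and an IDMC reviews accruing data (Protocol 6.7). The re-administration item cannot affect a first SAE report, because the next dose is 16 or 24 weeks away and the report is due within 24 hours.

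All of this stands and limits the consequence. It does not remove the defect. The call to judgement comes with an instruction to sort by the two lists, and those lists conflict. The 24-hour rule is also a partial backstop. For an SAE that the investigator learns of after discontinuation, Protocol 11.3.2 asks for a report if the investigator considers it related. Protocol 11.4 allows ongoing events judged unrelated to be closed out, while related ones are followed where possible until they resolve or stabilise.

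**Conclusion.** The point holds as a contradiction within the protocol's causality rules. The lists are not mutually exclusive, no precedence is given, and novelty or non-reappearance is each sufficient alone for Not related. A novel serious reaction with plausible timing and no other ready cause can be classed either way. If it is classed Not related, it is outside the SUSAR definition and the drug-related TEAE tables.

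The size is 13 of 16 logical profiles meeting both lists. This rests on reading each 'or' as printed and on counting profiles equally. A reader might take it to mean that most events are ambiguous, but the documents give no event frequencies, so that does not follow. Sponsor notification of SAEs under the 24-hour rule and the all-causality tables do not depend on these lists.

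This is more than missing detail, because a printed rule lets a reaction be called unrelated for being new. It should be corrected.

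**What to change.** Reconcile Protocol 11.1.4 and 11.2.2 as follows.

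1. Remove the known-pattern and re-administration items as stand-alone grounds for Not related, and keep them only as supporting considerations. A novel event with plausible timing and no ready alternative cause then meets only Related.
2. Add one sentence saying how to classify an event that still meets both lists. It should not let timing alone override every alternative cause. Allowing Not related only when no Related item is met would make 13 + 1 = 14 of the 16 profiles Related, and the drug-related tables would then discriminate very little.

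The cost is protocol and eCRF-guideline wording, and some more events classed as related.

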11.2.3. Structured Causality Assessment for Suspected Drug-induced Liver Injury

In the specific case of causality assessment for possible drug-induced liver injury, decision making is based on compatible clinical course, typical changes in hepatic biochemistry and careful, systematic exclusion of all other reasonable causes such as the following: viral hepatitis (including consideration of cytomegalovirus and Epstein-Barr virus), non-alcoholic or alcoholic fatty liver disease, autoimmune hepatitis, hypotension, heart failure, sepsis, biliary tract obstruction, including gallstone disease, portal vein thrombosis, metabolic or hereditary liver diseases (e.g., Wilson’s disease), and other hepatotoxic drugs [Aithal *et al*, 2011].

Comprehensive causality assessment for possible drug-induced liver injury should utilise expert opinion with formal hepatology or gastroenterology expertise as much as possible, particularly in any severe cases, ideally blinded to treatment assignment in line with published recommendations [Regev, 2014].

In all cases, structured causality assessment should consider the following: history and concomitant diseases, temporal relationship with study drug, including latency to time from first drug exposure to qualifying laboratory tests or compatible symptoms, which include the following: increasing fatigue; anorexia; nausea; vomiting; right upper quadrant pain; pattern of injury (hepatocellular, cholestatic, or mixed) based on the first set of laboratory tests that meet the threshold for possible drug-induced liver injury and using the R value; injury severity, including peak values and assessment of hepatic synthetic function (prothrombin time/international normalised ratio and albumin);

Study Number: SLN360-002	Compound No.: SLN360
Protocol	Version: 1.0

washout data, i.e., the resolution and time taken to reach a reduction in serum enzymes to $\geq 50\%$ peak and return to baseline; exclusion of other potential causes of liver injury with appropriate diagnostic evaluation (e.g., viral hepatitis serology, autoimmune hepatitis serology, imaging, and histology, if available); and clinical outcome [Chalasani *et al*, 2014].

11.3. Safety Reporting

11.3.1. Reporting Adverse Events

All medical and psychiatric conditions (except those related to the indication under study) present at screening will be documented in the medical history eCRF. Changes in these conditions and new symptoms, physical signs, syndromes or diseases should be noted on the eCRF during the rest of the study. Clinically significant laboratory abnormalities should also be recorded as AEs.

Wherever possible, a specific disease or syndrome rather than associated signs, symptoms, or abnormal assessments or laboratory findings should be identified by the Investigator and recorded on the eCRF. However, if an observed or reported sign or symptom is not considered a component of a specific disease or syndrome by the Investigator, it should be recorded as a separate AE on the eCRF.

Surgical procedures not prohibited in the eligibility criteria that were planned before enrolment in the study are not considered AEs, if the conditions were known before study inclusion. The medical condition(s) necessitating the surgical procedure should be reported in the patient's medical history.

Each AE is to be documented on the eCRF with reference to the date of onset, duration, frequency, severity, relationship to study drug, action taken with study drug, treatment of event and outcome. Furthermore, each AE is to be classified as being serious or non-serious. Changes to AEs and resolution dates are to be documented on the eCRF.

When changes in the intensity of an AE occur more frequently than once a day, the maximum intensity for the event should be noted. If the intensity category changes over time, then those changes should be recorded separately (with distinct onset dates).

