6.5. Safety Procedures

6.5.1. Adverse Event Assessments

Information regarding the occurrence of AEs for each participant will be collected from the time a signed and dated ICF for the main study is obtained until completion of the participant's last study-related procedure, which may include contact to follow-up for safety. Adverse events that start from the time the participant signs the main study ICF until treatment administration on Day 1 will be assigned as non-treatment emergent AEs; AEs starting or worsening after treatment administration will be recorded as TEAEs. See the Time and Events tables ([Appendix 15.1](#) and [Appendix 15.2](#)) for detailed timing of assessments. Grading of AEs is outlined in [Section 11.2](#).

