6.5.2. Injection Site Reaction Assessment

The monitoring of AEs will include special attention paid to potential ISRs. The position of the injection sites should be marked at the time of dosing and injection sites monitored throughout the study. Inspection of the site of administration and surrounding area will be performed at timepoints specified in the Time and Events tables ([Appendix 15.1](#) and [Appendix 15.2](#)). Injection site reactions should be followed up until resolution. Should an ISR not be resolved at the end of a study visit, the Investigator should maintain frequent contact, either in person or remotely, with the patient to confirm the course and the date of resolution. Additional evaluations of the injection site may be performed if a reaction is observed, at the discretion of the Investigator. The following information will be collected at all ISR assessments:

- Pain: Yes/No
- Tenderness: Yes/No
- Redness/erythema: Yes/No
 - If 'Yes', measurement of the largest dimension to be recorded in centimetres
- Swelling/induration: Yes/No
 - If 'Yes', measurement of the largest dimension to be recorded in centimetres

Study Number: SLN360-002	Compound No.: SLN360
Protocol	Version: 1.0

All ISRs are to be recorded as an AE if they meet AE criteria and an overall rating for each ISR will be recorded using the specific scale described in NCI-CTCAE v5 ([Table 6](#)).

Table 6 Injection site reaction grading scale

	Grade 1	Grade 2	Grade 3	Grade 4	Grade 5
Injection site reaction (ISR)	Tenderness with or without associated symptoms (e.g., warmth, erythema, itching)	Pain; lipodystrophy; oedema; phlebitis	Ulceration or necrosis; severe tissue damage; operative intervention indicated	Life-threatening consequences: urgent intervention indicated	Death

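### SAP 3.5.1 defines treatment-emergent AEs by start date alone; with each grade change recorded separately, a pre-dose AE that eases after dosing can be tabulated as a TEAE and one AE can count as several events

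*Protocol*

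**What the plan says.** On recording, protocol 11.3.1 states: "If the intensity category changes over time, then those changes should be recorded separately (with distinct onset dates". The only limit on splitting is for rapid fluctuation: "When changes in the intensity of an AE occur more frequently than once a day, the maximum intensity for the event should be noted". Slower changes are split, whichever way the grade moves.

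On treatment emergence, protocol 6.5.1 states: "AEs starting or worsening after treatment administration will be recorded as TEAEs". It also collects AEs from signature of the main consent form and classes those starting before the Day 1 dose as not treatment-emergent. SAP 3.5.1 is shorter: "Treatment emergent adverse events (TEAEs) are defined as AEs that start after the first dose of study drug". SAP section 6 reports no changes from the protocol's analyses.

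On counting, SAP 3.5.1 says "An overview of TEAEs will be provided including counts and percentages of subjects (and event counts) with the following". It then asks for summary tables with "the number and percentage of subjects with adverse events and the number of events classified by primary system organ class, and preferred term". Neither document defines an event for this purpose, and neither says how separate entries for one AE are joined.

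**The concern.** Each rule is workable alone; the difficulty comes from combining them. An entry made because an AE became milder has its own onset date. If that date falls after the first dose, the entry meets the SAP's TEAE definition, although the AE began before treatment and is improving. Protocol 6.5.1 would not class it as treatment-emergent.

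Separately, an AE that moves between grades leaves several entries. Without a linking rule, the direct way to fill an event-count column is to count entries.

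What is at stake is the meaning of the event-count columns and, for AEs that straddle the first dose, the participant counts as well. Some improvements could be displayed as harm arising on treatment.

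**Working it through.** Neither document gives a figure that bears on this, so there is nothing to reproduce. The check applies the written rules to constructed cases and then shows how the size depends on unknown quantities.

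**Step 1. Apply the recording rule.** Take three constructed AEs, one participant each.

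| AE | Course | Entries under protocol 11.3.1 | Entries starting after first dose |
|---|---|---|---|
| A | Starts after dosing; Grade 1, 2, 1 | 3 | 3 |
| B | Starts before dosing at Grade 2; eases to Grade 1 afterwards | 2 | 1 |
| C | Starts before dosing at Grade 1; worsens to Grade 2 afterwards | 2 | 1 |

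**Step 2. Count TEAEs under each reading.**

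| Reading | A | B | C | Events | Participants |
|---|---|---|---|---|---|
| SAP start-date rule, each entry taken as an AE | 3 | 1 | 1 | 5 | 3 |
| SAP start-date rule, entries linked | 1 | 0 | 0 | 1 | 1 |
| Protocol 6.5.1 (starts or worsens), entries not linked | 3 | 0 | 1 | 4 | 2 |
| Protocol 6.5.1, entries linked | 1 | 0 | 1 | 2 | 2 |

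The SAP definition departs from protocol 6.5.1 on either reading. Applied to entries, it admits the improvement (B). Applied to linked AEs, it loses the worsening (C). Linking and the worsening condition are therefore both needed.

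**Step 3. Size of the effect on event counts.** Let f be the share of AEs that change grade and k the number of changes in each of those. If entries are counted, the ratio of events to AEs is 1 + f × k. The documents give neither f nor k, so these values are assumptions:

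| f | k = 1 | k = 2 |
|---|---|---|
| 10% | 1.1 | 1.2 |
| 30% | 1.3 | 1.6 |
| 50% | 1.5 | 2.0 |

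If f and k are the same in two arms, the ratio of event counts between them is not distorted. If f were 30% in one arm and 10% in another, with k = 2 in both, the ratio would be distorted by 1.6 / 1.2 = 1.33. Nothing in the documents establishes such a difference.

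**Step 4. Size of the effect on participant percentages.** Only AEs like B matter here. Each such participant with no other TEAE adds 1/40 = 2.5 percentage points to the any-TEAE figure in an arm of 40, or 1/20 = 5 points in a single placebo group of 20. How many there would be is unknown.

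**Step 5. What does not change.** For an AE like A, the participant is counted once and the maximum is Grade 2, whether or not the entries are joined.

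**The case against.** The best defence is that the SAP speaks of events, not entries. Protocol 11.3.1 can be read as separating an event from the changes noted within it, and SAP section 7 defers detail to programming specifications that are not available here and could join the entries. This stands in part: counting entries as events is an inference from the missing rule, not something the SAP states.

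The protocol also excludes improvement in several places. Protocol 11.1.1 requires a condition present at screening to worsen before it is an AE, 6.5.1 requires starting or worsening, and 12.4.4.2.1 refers to AEs that have worsened. A reader may conclude that the SAP sentence is only shorthand. But it is the SAP's explicit definition, it sits beside a declaration of no changes, and protocol section 12 promises that the SAP will contain the derivation algorithms. A programming document should not have to override it.

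Two stronger readings are tempting and not supported. A reader might infer that one serious event would be counted as several serious TEAEs. Protocol 11.3.2 has progression of a serious event reported as follow-up to the original episode. That rule governs expedited reporting rather than tabulation, but it leaves the multiplication unestablished. A reader might also infer that injection-site reactions would inflate the active arms, since "Injection site reactions should be followed up until resolution". Yet protocol 6.5.2 gives each reaction one overall rating, and SAP 3.5.5 tabulates the local signs per participant by visit. Neither the inflation nor a difference between arms is shown.

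The consequences are also bounded. Safety is descriptive with no formal testing, the protocol's main AE unit is the participant, and conditions present at screening go to medical history, which narrows the pool of AEs that straddle the first dose.

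**Conclusion.** The point holds as an inconsistency between written rules. Read literally, protocol 11.3.1 and SAP 3.5.1 together class an improving pre-dose AE as treatment-emergent, contrary to protocol 6.5.1, and the SAP declares no change. In addition, without a linking rule, one AE with changing grade can be counted as several events.

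The documents do not support the statement that event counts will be inflated by a known amount, or unequally between arms. The multipliers of 1.1 to 2.0 rest wholly on assumed frequencies and on entries being counted as events. The effect is confined to event-count columns and, for participant counts, to AEs that began before dosing and eased afterwards. It is worth settling before database lock, because a choice made later would alter the safety counts by arm after the data are known.

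**What to change.** Make two changes in SAP 3.5.1, together:

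- Define a TEAE as an AE that starts after the first dose, or that began earlier and after the first dose reaches a grade higher than its pre-dose grade. This restores agreement with protocol 6.5.1.
- State that consecutive entries for the same AE are linked and counted as one event, at the maximum post-dose grade, in every event count. Linking can use an eCRF identifier or, failing that, the same participant and preferred term with adjoining stop and start dates.

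The cost is a short derivation and, at most, one link field on the AE form. Event counts would be somewhat smaller. Date-based linking could occasionally merge two distinct AEs that adjoin, which an identifier would avoid.
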